11.1.2 Disease Parameters

Measurable disease. Measurable lesions are defined as those that can be accurately measured in at least one dimension (longest diameter to be recorded) as ≥ 20 mm with conventional techniques (CT, MRI, x-ray) or as ≥ 10 mm with spiral CT scan. All tumor measurements must be recorded in millimeters (or decimal fractions of centimeters).

Note: Tumor lesions that are situated in a previously irradiated area might or might not be considered measurable.

Non-measurable disease. All other lesions (or sites of disease), including small lesions (longest diameter <20 mm with conventional techniques or <10 mm using spiral CT scan), are considered non-measurable disease. Bone lesions, leptomeningeal disease, ascites, pleural/pericardial effusions, lymphangitis cutis/pulmonis, inflammatory breast disease, abdominal masses (not followed by CT or MRI), and cystic lesions are all non-measurable.

Target lesions. All measurable lesions up to a maximum of 5 lesions per organ and 10 lesions in total, representative of all involved organs, should be identified as **target lesions** and recorded and measured at baseline. Target lesions should be selected on the basis of their size (lesions with the longest diameter) and their suitability for accurate repeated measurements (either by imaging techniques or clinically). A sum of the longest diameter (LD) for all target lesions will be calculated and reported as the baseline sum LD. The baseline sum LD will be used as reference by which to characterize the objective tumor response.

Non-target lesions. All other lesions (or sites of disease) including any measurable lesions over and above the 10 target lesions should be identified as **non-target lesions** and should also be recorded at baseline. Measurements of these lesions are not required, but the presence or absence of each should be noted throughout follow-up.

11.1.3 Methods for Evaluation of Measurable Disease

CT will be used for all evaluations.

11.1.4 Response Criteria

Subjects will be monitored for recurrence, not response, and thus no formal response criteria will be employed.

11.1.5 Relapse-Free Survival

Relapse-Free Survival is defined as the time from surgical excision of CRCLM to evidence of definite recurrence, as determined by the treating physician.

12. DATA REPORTING REQUIREMENTS / STUDY AND DATA MANAGEMENT

12.1 Training of Study Site Personnel

Before the first subject is entered into the study, a MedImmune representative will review and discuss the requirements of the Clinical Study Protocol and related documents with the investigational staff and also train them in any study-specific procedures and system(s) utilized.

The principal investigator will ensure that appropriate training relevant to the study is given to all of these staff, and that any new information relevant to the performance of this study is forwarded to the staff involved. The principal investigator will maintain a record of all individuals involved in the study (medical, nursing and other staff).

12.2 Monitoring of the Study

During the study, a MedImmune representative will have regular contacts with the study site, including visits to:

- Provide information and support to the investigator(s).
- Confirm that facilities remain acceptable.
- Confirm that the investigational team is adhering to the protocol, that data are being accurately and timely recorded in the eCRFs, that biological samples are handled in accordance with the Laboratory Manual and that study drug accountability checks are being performed.
- Perform source data verification (a comparison of the data in the eCRFs with the subject's medical records at the hospital or practice, and other records relevant to the study) including verification of informed consent of participating subjects. This will require direct access to all original records for each subject (eg, clinic charts).
- Ensure withdrawal of informed consent to the use of the subject's biological samples is reported and biological samples are identified and disposed of/destroyed accordingly, and the action is documented, and reported to the subject.

The MedImmune representative will be available between visits if the investigator(s) or other staff at the center needs information and advice about the study conduct.

12.2.1 Source Data

Refer to the Clinical Study Agreement for location of the source data.

12.2.2 Study Agreements

The principal investigator at each/the center should comply with all the terms, conditions, and obligations of the Clinical Study Agreement, or equivalent, for this study. In the event of any inconsistency between this Clinical Study Protocol and the Clinical Study Agreement, the terms of Clinical Study Protocol shall prevail with respect to the conduct of the study and the treatment of subjects and in all other respects, not relating to study conduct or treatment of subjects, the terms of the Clinical Study Agreement shall prevail.

Agreements between MedImmune and the principal investigator must be in place before any study-related procedures can take place, or subjects are enrolled.

12.2.3 Archiving of Study Documents

The investigator follows the principles outlined in the Clinical Study Agreement.

12.3 Study Timetable and End of Study

An individual subject will be considered to have completed the study if the subject was followed through the DLT-evaluation period or experienced a DLT during the DLT-evaluation period (for subjects in the dose-exploration phase) or the subject completed at least 1 on-treatment disease evaluation (for subjects in dose-expansion phase) regardless of the number of doses of investigational product that was received. The end of the study ("study completion") is 5 years after the final subject is enrolled or the date the study is closed by the sponsor, whichever occurs first.

12.4 Data Management

Data management will be performed according to the Data Management Plan.

A Web Based Data Capture system will be used for data collection and query handling. The investigator will ensure that data are recorded on the eCRFs as specified in the study protocol and in accordance with the instructions provided.

The investigator ensures the accuracy, completeness, and timeliness of the data recorded and of the provision of answers to data queries according to the Clinical Study Agreement. The investigator will sign the completed eCRFs. A copy of the completed eCRFs will be archived at the study site.

13. STATISTICAL CONSIDERATIONS

13.1 Endpoints

1. Primary Endpoints

- Feasibility will be assessed by whether or not the patient successfully goes to surgery following the planned treatments, scans, and biopsy.
- Safety will be assessed by CTCAE version 4.03 for cohort A and 5.0 for cohorts B and C.

2. Secondary Endpoints

- Various immune parameters
- Response - irRECIST
- Overall survival (OS) measured from the date of study entry until death from any cause
- Relapse-free survival (RFS) from the date of study entry until relapse or death from any cause

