1.2. Secondary Objectives

1. Explore the changes in various immune parameters, including PD-L1 and PD-1 expression in the tumor, over treatment and correlate with response and survival with goal of biomarker discovery.
2. Estimate the relapse-free survival (RFS) in all enrolled subjects.

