5.4 Duration of Follow Up

Patients may be followed for up to 2 years from liver surgery or until death, whichever occurs first. Patients removed from study for unacceptable adverse events will be followed until resolution or stabilization of the adverse event.

Note after one year of follow-up without recurrence schedule of follow-ups can be adjusted according to standard of care. This will take precedence over the study calendar.

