7.4.1 Time Period for Collection of Adverse Events

Adverse events will be collected from time of signature of informed consent, enrollment, randomization, throughout the treatment period and including the follow-up period of 90 days after the last dose of Durvalumab post-operatively. Serious adverse events will be recorded from the time of informed consent signature through 90 days after the last dose of Durvalumab.

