13.3 Interim Monitoring

A Bayesian sequential monitoring design[66, 67] will be used to monitor the trial for surgery and toxicity rates. Generally, interim analyses will begin after 3 patients become evaluable, and will then be performed continuously to ensure that patients are exhibiting reasonable toxicity and surgery rates to continue the trial. Specific rules are in each subsection below. Since 1-2 patients are expected to be enrolled each month, monitoring data will be kept up-to-date and the tables below checked prior to consenting each patient once the 3rd patient in each cohort has been on study 4 weeks after the first dose of Durvalumab. Enrollment will not need to wait for the previous patient to become evaluable, but the rules will be checked for all evaluable patients before consenting each patient. This includes a risk of 1-2 patients entering on the study beyond the designed stopping rules, which is considered a reasonable risk. If accrual occurs faster than 1-2 patients per month, this practice will be reconsidered. All calculations for stopping boundaries and operating characteristics were performed in Multicenter Lean Desktop v2.1.

Patients will be evaluable once they have received the first dose of Durvalumab/tremelimumab, durvalumab/oleclumab or durvalumab/monalizumab and have then had 8 weeks time to go to surgery. If surgery has not occurred by 8 weeks then for monitoring these patients will have been considered not to have gone to surgery even if they do after 8 weeks. Patients will be allowed up to 12 weeks to complete surgical resection. If surgical resection is not done within 12 weeks from then patient will be removed from clinical trial

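### RFS has two conflicting current definitions, of which only that in 13.1 fits the objective, and unresected patients have no specified relapse or survival follow-up beyond the safety window

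*Combined protocol and SAP*

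**What the plan says.** The objective in Section 1.2 is: "Estimate the relapse-free survival (RFS) in all enrolled subjects". Two sections then define the endpoint.

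- Section 13.1: "Relapse-free survival (RFS) from the date of study entry until relapse or death from any cause". Overall survival (OS) in the same list also starts at study entry.
- Section 11.1.5: "Relapse-Free Survival is defined as the time from surgical excision of CRCLM to evidence of definite recurrence, as determined by the treating physician".

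On what is monitored, Section 11.1.4 states: "Subjects will be monitored for recurrence, not response, and thus no formal response criteria will be employed". Section 11.1.1 adds a set evaluable for recurrence, which needs baseline measurable disease, at least one cycle and a re-evaluation, but not resection.

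On follow-up, Section 13.3 states: "If surgical resection is not done within 12 weeks from then patient will be removed from clinical trial". Section 5.4 (Duration of Follow Up) states: "Patients may be followed for up to 2 years from liver surgery or until death, whichever occurs first". Table 10.1 ends at resection, and the four-monthly visits and CT appear only in Tables 10.2 and 10.3, both headed as post-resection calendars. Section 13.4 names Kaplan-Meier for OS and RFS and gives no censoring rule.

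**The concern.** The two definitions differ in time origin and in event set, so two analysts who each follow a current section would report different RFS from the same data. Choosing 13.1 does not settle everything. It does not say whether progression before surgery is a relapse, and the data needed for patients who never reach surgery are not scheduled.

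Those patients are unlikely to be a random subset. Section 2.6 reports that 3 of the first 14 patients to reach the point of surgery were not resected, 2 of them because of progression. OS from study entry has the same follow-up gap. At stake is a descriptive secondary estimate, but Section 13.4 says the results will be used to design the next trial.

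**Working it through.** **Text side by side**

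- Origin: study entry (13.1) against excision (11.1.5). Only the first exists for every enrolled patient.
- Event: relapse or death (13.1) against definite recurrence (11.1.5).
- Progression before surgery: 11.1.4, and the opening of Section 11 with its post-operative aim of no evidence of disease, lean towards post-resection recurrence. Section 11.1.1 does not require resection. The point is undecided.
- Follow-up of unresected patients: removal at 12 weeks, a clock tied to liver surgery, and later calendars for resected patients only. What remains is safety follow-up to 90 days after the last dose (90/7 = 12.9 weeks).

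**How many patients.** At the 80% surgery rate of Section 13.2, 0.20 × 25 = 5 in cohort A and 0.20 × 15 = 3 in each of B and C are unresected, or 11 of 55.

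**Size, as an illustration.** The plan gives no RFS figure to reproduce.

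From the documents:
- 20% unresected.
- Surgery w weeks after dosing, with w from 3 (Section 5.1) to 12 (Section 13.3). Section 5.1 itself stops at 10 weeks; 12 covers both.
- p = 2/3 of unresected patients progressing before surgery (2 of 3; exact 95% interval 9% to 99%).

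Assumed:
- 12-month RFS from resection R = 0.60, with exponential decline.
- 12-month survival of unresected patients S = 0.50 to 0.80.
- Resected patients event-free until surgery.
- Time zero at first dose. Entry may be up to about two weeks earlier, since screening runs from D-14.
- Death without recurrence is not modelled separately: the same R serves both definitions.

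RFS of resected patients 12 months from time zero is R^((52−w)/52) = 0.618 (w=3) or 0.675 (w=12).

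1. Section 11.1.5: 0.60.
2. Section 13.1, pre-operative progression counted: 0.8 × R^((52−w)/52) + 0.2 × (1−p) × S. Lowest: 0.8 × 0.618 + 0.2 × (1/3) × 0.50 = 0.528. Highest: 0.8 × 0.675 + 0.2 × (1/3) × 0.80 = 0.593.
3. Section 13.1, only deaths counted in unresected patients: 0.8 × R^((52−w)/52) + 0.2 × S = 0.594 to 0.700.
4. Section 13.1, unresected patients censored at week 12: 0.8 × R^((52−w)/52) + 0.2 × R^(40/52) = 0.629 to 0.675, where R^(40/52) = 0.675.

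Against 0.60 these are −7 to −1, −1 to +10, and +3 to +8 points. With R from 0.40 to 0.70 they widen to −10 to +5, −3 to +16, and +2 to +9 points.

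**Direction of censoring at removal.** Censoring gives the unresected fifth a value of 0.675.
- Progression counted: their value is S/3 = 0.167 to 0.267, so censoring raises RFS by 0.2 × (0.675 − 0.267) = 8 to 0.2 × (0.675 − 0.167) = 10 points.
- Deaths only: their value is S, so censoring raises RFS if S is below 0.675 and lowers it if above. At S = 0.80 and w = 3 it gives 0.629 against 0.654.

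**Sampling error.** 1.96 × √(0.6 × 0.4/n) = 0.192 (n=25) or 0.248 (n=15).

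**The case against.** The strongest reply is that a competent analyst would use 13.1: it is in the statistical section, matches Section 1.2, shares the OS origin, and feeds 13.4. That stands, and it is why 11.1.5 is the text to correct. It does not resolve the status of pre-operative progression or supply the missing follow-up.

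A second reply is that unresected patients are followed. In part they are. Section 7.4.1 says: "Serious adverse events will be recorded from the time of informed consent signature through 90 days after the last dose of Durvalumab"; deaths are reportable over the same window (Section 7.6.1.2); and Section 5.4 adds: "Patients removed from study for unacceptable adverse events will be followed until resolution or stabilization of the adverse event". A reader might infer that these patients get no follow-up at all, and the documents do not support that. But none of this yields relapse or longer-term survival data. The words on following until death in Section 5.4 are permissive and sit in a sentence timed from liver surgery. The five-year end of study in Section 12.3 sets no patient contacts.

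A reader might also infer that censoring at removal must inflate RFS. The documents do not support that either. No censoring rule is stated, and under the deaths-only reading the direction depends on how long unresected patients survive.

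Finally, RFS is secondary and untested, and the shifts lie inside sampling error. That limits the importance of the point, although a systematic difference does not average out as random error does.

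**Conclusion.** The point holds and should be fixed before analysis. The 11.1.5 definition conflicts with 13.1 and cannot meet the objective. Under 13.1 the status of pre-operative progression is open, and beyond the 90-day safety window no relapse or survival follow-up is specified for about one patient in five.

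The size is illustrative only: several points either way under assumed rates, inside sampling error of about ±19 to 25 points. It rests on the assumed R and S, on a two-thirds progression share taken from 3 patients, and on leaving deaths without recurrence out of the comparison. If pre-operative progression is an event, censoring at removal biases RFS upward at that share; if only deaths count, the direction is not fixed. The primary feasibility and safety results and the sample sizes are not affected.

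**What to change.** 1. Replace the definition in 11.1.5 with that of 13.1: all enrolled patients, from study entry, death from any cause counted. Reconcile the evaluable-for-recurrence set in 11.1.1 with it. State before analysis whether progression before surgery is an event, and by what criterion. Counting it is recommended so that the endpoint covers all enrolled patients, though it is not the only defensible choice. Report any from-resection RFS in resected patients under a separate name.
2. In 13.4, state that event-free patients are censored at the last disease assessment, not at removal for non-resection.
3. In 13.3, state that removal ends protocol treatment but not collection of progression and vital status from routine records. This also closes the gap for OS.
4. In 5.4, keep the two-year clock from liver or lung resection for resected patients, and use study entry for unresected patients. Counting from entry for everyone would shorten post-resection follow-up. The present wording gives no clear clock after a lung-only resection.

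Cost: wording in five sections (5.4, 11.1, 13.1, 13.3, 13.4) and status for about 3 to 5 patients per cohort. In cohort A, which Section 13.2 expected to have about 25 patients enrolled by the time of this revision, part of this is retrospective and may be incomplete. The RFS estimate may look less favourable. No treatment rule or sample size changes.

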13.2 Sample Size Justification

Sample sizes of 15 and 25 patients, are driven by safety and feasibility endpoints. The selection of 25 patients in cohort A ensures that if the trial continues to full size, a posterior 95% credible interval (ci) of surgery received will be (0.62, 0.92), assuming that the proportion of patients successfully getting to surgery is 80%, with a prior of beta(1.2, 0.8) and 20 patients getting to surgery. Cohorts B and C will enroll 15 patients, which will ensure that a posterior 95% credible interval (ci) of surgery received will be (0.57, 0.94), assuming that the proportion of patients successfully getting to surgery is 80%, with a prior of beta(1.2, 0.8) and 12 patients getting to surgery. The smaller number in cohorts B and C are due to feasibility constraints of accrual rate and overall trial budget. We expect to enroll approximately 25 patients in Cohort A by the time this protocol revision is approved.

In order to ensure a homogenous population clinical trial will require that at least 66% of patients have pre-treatment with either no chemotherapy or oxaliplatin-based chemotherapy. The use and type of per-operative therapy prior to enrollment in this clinical trial will be monitored.

13.3 Interim Monitoring

A Bayesian sequential monitoring design[66, 67] will be used to monitor the trial for surgery and toxicity rates. Generally, interim analyses will begin after 3 patients become evaluable, and will then be performed continuously to ensure that patients are exhibiting reasonable toxicity and surgery rates to continue the trial. Specific rules are in each subsection below. Since 1-2 patients are expected to be enrolled each month, monitoring data will be kept up-to-date and the tables below checked prior to consenting each patient once the 3rd patient in each cohort has been on study 4 weeks after the first dose of Durvalumab. Enrollment will not need to wait for the previous patient to become evaluable, but the rules will be checked for all evaluable patients before consenting each patient. This includes a risk of 1-2 patients entering on the study beyond the designed stopping rules, which is considered a reasonable risk. If accrual occurs faster than 1-2 patients per month, this practice will be reconsidered. All calculations for stopping boundaries and operating characteristics were performed in Multicenter Lean Desktop v2.1.

Patients will be evaluable once they have received the first dose of Durvalumab/tremelimumab, durvalumab/oleclumab or durvalumab/monalizumab and have then had 8 weeks time to go to surgery. If surgery has not occurred by 8 weeks then for monitoring these patients will have been considered not to have gone to surgery even if they do after 8 weeks. Patients will be allowed up to 12 weeks to complete surgical resection. If surgical resection is not done within 12 weeks from then patient will be removed from clinical trial

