5. TREATMENT PLAN

5.1 Study Design and Duration

This study is an open-label, single center trial assessing the safety and feasibility of using perioperative neoadjuvant and adjuvant immune-therapy for resectable liver or lung metastases.

Cohort A will consist of neoadjuvant tremelimumab 75 mg IV flat dose and durvalumab 1500 mg IV flat dose. Adjuvant therapy will consist of 4 monthly doses of durvalumab 1500mg IV.

Cohort B will consist of neoadjuvant oleclumab 3000 mg IV flat dose followed by durvalumab 1500 mg IV flat dose. Adjuvant therapy will consist of 4 months of oleclumab every two weeks at 3000 mg IV flat dose and durvalumab every 4 weeks at 1500 mg IV flat dose. On days oleclumab and durvalumab are both administered, oleclumab will be given first (see Section 8.1.4).

Cohort C will consist of neoadjuvant durvalumab 1500 mg IV flat dose then Monalizumab 750mg IV flat dose. Adjuvant therapy will consist of 4 months of durvalumab 1500 mg IV flat dose and monolizumab 750 mg, both administered every four weeks.

[figure not shown]
Cohort A has been enrolling since the study initiation and will enroll up to 25 patients. At the time of amendment activation initially opening, cohort B may enroll 5 patients followed by 5 patient enrollment for cohort C. Enrollment will continue in this alternating manner with approximately 5 patient blocks at a time for these cohorts. Enrollment may be adjusted based on Medimmune/MD Anderson determined priorities and drug availability. Cohort B and C will each be 15 patients.

[figure not shown]

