13.3.1 Interim Analyses for Futility per cohort

For futility, the trial will be stopped early if $\Pr[\theta_s < 0.60 \mid \text{data}] > 0.90$, where θ_s denotes the proportion of patients who successfully receive surgery. That is, given the outcomes from the patients who have already been evaluated, if it is determined that there is a more than 90% chance that the surgery rate is 60% or less, the trial will be stopped for futility. Assuming a prior distribution of θ_s of $\sim \text{beta}(1.2, 0.8)$ for this experimental treatment against a constant 60%, pre-defined stopping boundaries corresponding to this probability criterion are provided in the following table. Once 3 patients have been enrolled in a cohort, follow the instructions in this table according to the schedule described above.

If there are this many (or more) patients whose surgery status is determined	Stop if there are this many or fewer patients who received surgery	If there are this many (or more) patients whose surgery status is determined	Stop if there are this many or fewer patients who received surgery
3	0	15*	6
5	1	17	7
7	2	19	8
9	3	20	9
11	4	22	10
13	5	24	11

* Cohorts B and C will stop at 15 patients regardless of the number of patients who received surgery

Three patients will be accrued first. If 0 of the 3 patients receive surgery in a given cohort as scheduled, the cohort should be stopped and the treatment will be declared as not feasible for this population. If there is at least 1 patient with surgery, the next patient will be entered in the study, unless the trial needs to stop according to the toxicity boundaries below. Check continuously as described above for sufficient surgery rate assuming the trial does not stop for toxicity first. The operating characteristics for futility and toxicity are summarized below the toxicity rules.

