13.3.2 Interim Analyses for Toxicity

Under the same model described for futility, toxicities will be monitored assuming a prior probability of toxicity following $\text{Beta}(0.6, 1.4)$ in the current treatment arm against a constant rate of 0.30. Based on a previous study, we assume that a 15% rate of toxicity events would be acceptable and a 30% rate of toxicity would be unacceptable. [68] For trial monitoring and decisions about future trials, extreme toxicities (TOX) will be defined as any grade 3 or higher adverse event that is possibly, probably, or definitely related to any therapy received on this protocol and occur between the first dose of Durvalumab and surgery (or 4 weeks after that dose if the patient does not receive surgery as scheduled) with the following exception. Any grade 3 adverse event that is

potentially treatable with steroids will only count as an extreme toxicity if it does not improve to grade 2 or better within 2 weeks. Grade 3 nausea or vomiting that responds to anti-emetics within 72 hours and asymptomatic grade 3 or 4 lipase or amylase elevations will not count as TOX. The trial will be terminated if $\text{Prob}(\Theta_{\text{TOX}} > 0.30 | \text{data}) > 0.9$, where Θ_{TOX} is the proportion of patients experiencing a TOX event. Following this rule, the trial will be terminated according to the following table once the first 3 patients are evaluable.

If there are this many patients (or more) with TOX	3	4	5	6	7	8	9	10	11
Stop the cohort if there are this many (or fewer) patients who are evaluable (have TOX or completed 4 weeks after first Durvalumab dose without TOX)	3	7	9	12	14	17*	20	22	25*

* Always stop with 25 patients in Cohort A, but if 11 or more patients have TOX, then this treatment regimen is too toxic for further use. Always stop at 15 patients in Cohorts B and C, but if 8 or more patients have TOX, then this regimen is too toxic for further use.

Three patients in each cohort will be accrued first. If 3 of the 3 patients have TOX, stop that cohort and the treatment will be declared as too toxic for that cohort. If there is at least 1 patient with surgery without TOX, the next patient will be entered in the study, unless the trial needs to stop according to futility boundaries above. Check continuously as described above for toxicity assuming the trial does not stop for futility first. The operating characteristics for the combined futility and toxicity are summarized in the following table

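### The overrun of one to two patients in 13.3 fits the 4-week toxicity outcome, but not the 8-week surgery outcome across the planned accrual range; the stopping rules are checked only before consent

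*Combined protocol and SAP*

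**What the plan says.** Section 13.3 sets the accrual expectation ("Since 1-2 patients are expected to be enrolled each month") and does not hold enrolment for pending outcomes: "Enrollment will not need to wait for the previous patient to become evaluable". The safeguard is that "the rules will be checked for all evaluable patients before consenting each patient". The accepted cost is one figure for both rules: "This includes a risk of 1-2 patients entering on the study beyond the designed stopping rules, which is considered a reasonable risk". The section does not show how the figure was obtained, or whether the accrual rate is per cohort or for the whole trial. It promises to reconsider only if accrual is faster than that range.

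The two rules mature at different times. A patient counts for toxicity on having a TOX event or having "completed 4 weeks after first Durvalumab dose without TOX" (13.3.2). For surgery, patients are evaluable once they have been dosed and "have then had 8 weeks time to go to surgery" (13.3). Section 13.4 recognises the difference by requiring futility data to be updated to week eight.

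Sections 13.3.1 and 13.3.2 describe the first look as an initial group of three, after which "If there is at least 1 patient with surgery, the next patient will be entered in the study". Section 5.1 has cohorts B and C take turns: "Enrollment will continue in this alternating manner with approximately 5 patient blocks at a time for these cohorts". It adds that enrolment may be adjusted for priorities and drug supply. Screening (5.1.1) runs from day -14 to day -1. Table 5.1-1 has eligibility confirmed again before the first dose; it does not mention the stopping boundaries.

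**The concern.** The overrun figure is the stated reason why not pausing is acceptable, so it should hold for both rules. Surgery matures twice as late as toxicity, yet both share one figure. If it was worked out on the shorter lag, the risk accepted for futility is understated at the faster end of the plan's own accrual range, where the promise to reconsider does not apply.

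Two gaps in wording bear on the same risk. A check made only at consent cannot catch a boundary crossed while a patient is in screening. And 13.3 says accrual need not wait, while 13.3.1 and 13.3.2 read as if patient 4 enters only after the first three have been looked at. At stake is how many patients enter a regimen that the rules have already rejected.

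**Working it through.** **Inputs.** Accrual of 1 to 2 a month (13.3); toxicity lag 4 weeks (13.3.2); surgery lag 8 weeks (13.3); screening up to 2 weeks (5.1.1); one month = 52/12 = 4.33 weeks.

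**Formula.** Expected patients pending = monthly rate × lag in weeks / 4.33, for continuous accrual to one cohort.

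| Lag | 1 a month | 2 a month |
|---|---|---|
| 4 weeks (toxicity, dosed) | 0.92 | 1.85 |
| 6 weeks (toxicity, plus 2 weeks of screening) | 1.38 | 2.77 |
| 8 weeks (surgery, dosed) | 1.85 | 3.69 |
| 10 weeks (surgery, plus 2 weeks of screening) | 2.31 | 4.62 |

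The plan's figure is reproduced by the first row. For surgery, two pending patients are reached at 2 × 4.33 / 8 = 1.08 a month, so the figure holds only at the slow end of the range.

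**First look, evenly spaced.** At 2 a month, patients 1 to 3 are dosed at months 0, 0.5 and 1.0. If none has surgery, patient 3's status is fixed at 1.0 + 8/4.33 = 2.85 months. Patients 4 and 5 (months 1.5 and 2.0) have been dosed. Under continuous accrual so has patient 6 (month 2.5), an overrun of 3. With a block of five the cohort has already handed over, and the overrun is 2.

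**Simulation.** The futility boundaries were recomputed from the beta(1.2, 0.8) prior and match the printed table. Arrivals were random at the stated rate. Overrun is the number of patients already in the cohort at a futility stop beyond those whose status was determined. The true surgery rates of 0.40 and 0.50 are assumptions.

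| Setting | Mean overrun, 1 to 2 a month | More than 2 patients |
|---|---|---|
| Continuous, rate 0.40, all outcomes known at week 8, no screening, N=25 | 1.8 to 3.5 | 27% to 69% |
| Same, with 2 weeks of screening | 2.2 to 4.5 | 38% to 83% |
| Continuous, rate 0.50, surgery known at weeks 3 to 8, non-surgery at week 8, screening 0 to 2 weeks | about 1.75 to 3.3 | at 2 a month: 61% (N=15), 65% (N=25) |
| Strict blocks of five, N=15, rate 0.40, all outcomes known at week 8, screening 0 or 2 weeks | 1.1 to 1.9 | 8% to 29% |
| Strict blocks of five, N=15, rate 0.50, timing as in row 3 | 1.0 to 1.5 | 7% to 18% |

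Under the timing of rows 3 and 5, not dosing anyone still in screening when a boundary is crossed would lower the overrun by about 0.1 to 0.4 patients per futility stop.

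**The case against.** The case for leaving the text alone has real weight.

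- **The figure can be right.** At 1 a month the 8-week lag gives 1.85. With strict blocks the mean stays between 1 and 2 at either rate. Both points stand, but 5.1 calls the blocks approximate and allows changes, so the cap is likely rather than assured.
- **Cohort A hardly matters now.** Section 13.2 expects about 25 patients in it by approval of this revision. The N=25 results therefore have little forward use; B and C are what count.
- **Eight weeks is a ceiling.** Resection is planned at about 3 weeks, and the three non-resections in 2.6 were due to progression or earlier liver toxicity, which could be known sooner. If successes are known at an assumed 3.5 weeks and failures at 8, the mean under continuous accrual is 1.4 to 2.7 (1.9 to 3.6 with screening). If failures are known at an assumed 4 weeks, it is 1.8 at 2 a month without screening. This reduces the excess, but 13.3 itself defines evaluability at 8 weeks.
- **A futility stop may be rare.** Section 2.6 reports 11 of 14 resected (79%). At a true rate of 0.80 a futility stop occurs in about 1% to 2% of simulated cohorts, an expected overrun of 0.01 to 0.04 patients per cohort. That is fair as to expected harm, but the accepted risk is about what happens when a boundary is crossed.
- **The first-look wording can be harmonised.** Section 13.3.1 refers back to the schedule in 13.3, so it need not impose a pause. But it can be read as one, and staff cannot tell whether patient 4 waits.

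A reader might also infer three stronger things that the documents do not support. The blocks of five do not worsen the overrun: outcomes mature while the other cohort accrues. The operating-characteristics table is not wrong: it reproduces with immediate outcomes (true toxicity 0.10, surgery 0.50, N=25: 0.592 and 16.2 against the printed 0.59 and 16.2), and 13.3 discloses entry beyond the rules separately. And no section says that a consented patient is dosed after a stop; the text is silent.

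**Conclusion.** The point stands in limited form. One overrun figure is applied to two outcomes with different lags. It is right for dosed patients on the 4-week toxicity outcome. For surgery it holds at about 1 a month, or on average if B and C alternate strictly in fives. It does not hold for continuous accrual to one cohort above about 1.1 a month, where the expected number rises to 3.7 dosed at 2 a month. The excess is therefore about one to two patients at the upper rate, and up to about three counting those in screening.

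This assumes that the whole stated rate goes to the open cohort and that non-surgery is known only at week 8. The simulated percentages are conditional on a futility stop and on the assumed surgery rates. The absence of a boundary check before dosing and the unclear status of patient 4 do not depend on any of these numbers.

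**What to change.** In 13.3:

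1. State the overrun by outcome, with its accrual assumption: about 1 to 2 patients for toxicity; for futility about 1 to 2 under strict alternation in fives, and about 2 to 4 if accrual to one cohort is continuous. Say whether the monthly rate is per cohort or trial-wide, and whether dosed or consented patients are counted.
2. Check both tables again before each patient's first dose, as well as before consent, and state how a patient who is consented but not yet dosed is handled if a boundary has been crossed.
3. Reconcile 13.3 with the first-look text in 13.3.1 and 13.3.2, so that one rule says whether patient 4 of a cohort waits.

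The cost is a few sentences and one more look at existing tables. The stated risk becomes slightly less favourable, and a consented patient may occasionally not be treated in that cohort. The boundaries, sample sizes and operating-characteristics table need no change on this account.
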